7.5 Follow-Up Procedures and Therapy Transitions

In this study, there are no specific follow-up procedures or therapy transitions required. Following study completion, subjects will return to their previous care provider.

Alcon products associated with device deficiencies and/or product-related AEs should, if possible, be returned to Alcon and must include the complaint number, which will be provided by the study Sponsor after the case is entered in the study Sponsor's Global Product Complaint Management System (GPCMS).

Return any recoverable Alcon Product associated with a product-related AE (adverse device effect [ADE], serious adverse device effect [SADE]) or device deficiency to the Sponsor. Procedures vary so Investigators must contact their assigned monitor for detailed guidance. Follow biohazard regulations if the product has touched the eye (i.e., place the product in a biohazard labeled bag). Include the SAE/ADE or device deficiency eCRF in the return package. Maintain a copy of shipment tracking information and all documents submitted with the product.

7.6 Study Timetable / Schedule of Events

A Schedule of Events is provided in the table below. Retrospective assessments will be performed by standard clinical practice of the respective country and the medical institution; however, for the prospective Visit 1, assessments should be conducted in the order set forth in Table 3.

Table 3. Schedule of Events

Event	Retrospective		Prospective	
	Preoperative and Operative Visit	Post-operative Standard of Care & Unplanned Visits	Visit 1 (3-5 Years +/- 90 Days Post-operative)	Unscheduled Visit ^a
Informed Consent			✓	
Eligibility Determination			✓	
Demographics			✓	
Medical History	✓ ^b			
Concomitant Medications	✓***	✓	✓	✓**
Biometry & Keratometry	✓			
Pre-operative Manifest Refraction	✓			
Predicted Residual Refractive Error	✓*			
Lens Model & Power	✓			
IOL Calculation Method	✓*			
Other Surgical Procedures During Cataract or Refractive Lens Exchange Surgery	✓*			
Visual Disturbances (QUVID)			✓	
Manifest Refraction	✓*	✓*	✓	
Binocular UCVA		✓†	✓	
Monocular BCDVA		✓†	✓	✓**
Binocular BCDVA		✓†	✓	
Binocular UCVA at 66 cm		✓†	✓	
Binocular DCVA at 66 cm		✓†	✓	
Binocular UCVA at 40 cm		✓†	✓	
Binocular DCVA at 40 cm		✓†	✓	
Slit Lamp Examination (Biomicroscopy)	✓	✓	✓	✓**
Posterior Capsule Opacification (PCO)			✓	✓**
Capsulotomy Assessment			✓	
Tonometry			✓	✓**
Dilated Fundus Examination			✓	✓**
Actual Axis of IOL Orientation	✓*	✓††	✓	
Assessment of Adverse Events	✓	✓	✓ ^c	✓**
Assessment of Device Deficiencies	✓*	✓*	✓	✓**
Study Exit			✓	✓**

^a Prospective visit after Visit 1 to monitor subjects with ongoing AEs

^b Medical history includes all relevant systemic and all ocular conditions that began prior to surgery and implantation of study IOL(s).

^c AEs should be assessed at all post-operative visits through Visit 1 and recorded in EDC.

* If available

** As needed

*** Do not enter medications used for cataract surgery in EDC

† Immediate post-operative visual acuity (1-6 months post-operative), if available

†† From 1 day post-operative visit, if available

7.7 Study Protocol Compliance / Treatment Adherence

Based on the study design, protocol compliance consists of completing all the prospective assessments, which are anticipated to require a single study visit. Subjects who decline to complete the prospective assessments will be withdrawn/exited from the study. Withdrawn subjects will not be replaced.

7.8 Deviations from the Clinical Protocol

The Investigator and site personnel should conduct the study in compliance with the protocol and should use continuous vigilance to identify and report protocol deviations. The Investigator may not deviate from the protocol, except when necessary to eliminate an immediate hazard to a study subject, or when the change involves only logistical or administrative aspects of the study. Any significant deviation from the protocol must be reported immediately to the Sponsor or Sponsor's representative and if applicable, to the relevant IRB/IEC, in accordance with the local regulation.

7.9 Subject Withdrawal

7.9.1 *Subject Withdrawals*

Subjects withdrawn or terminated early will continue to receive Standard of Care treatment. The termination of study participation is not anticipated to affect subject safety. Withdrawn subjects will not be replaced.

7.9.2 *Data Collection and Follow-Up for Withdrawn Subjects*

If a subject withdraws consent to participate in the study, or is withdrawn by the Investigator, reasons for withdrawal or early termination will be obtained whenever possible.

7.10 Subject Compensation

Subject compensation will be provided for the prospective visits.

7.11 Clinical Study Termination

The study Sponsor reserves the right to suspend or close the investigational site or suspend or terminate the study in its entirety at any time.

If the clinical study is prematurely terminated or suspended by the study Sponsor:

- The study Sponsor must:
 - Immediately notify the Investigator(s) and subsequently provide instructions for study termination.

- Inform the Investigator and the regulatory authorities of the termination/suspension and the reason(s) for the termination/suspension.
- The Investigator must:
 - Promptly notify the IRB/IEC of the termination or suspension and of the reasons.
 - Provide subjects with recommendations for post-study treatment options as needed.

The Investigator may terminate the site's participation in the study for reasonable cause.

8 DATA COLLECTION AND ANALYSIS

8.1 Subject Populations for Analysis

Subject populations for analysis include:

- Full Analysis Set (FAS) population: the FAS population will include all eyes of enrolled subjects who pass the screening. The FAS will be the primary population for all safety analyses and performance analyses.

8.2 Statistical Methods

There is no statistical hypothesis for the endpoints in this study. Appropriate descriptive statistics will be computed and presented for all categorical and continuous endpoints. A full description of statistical methods will be presented in the Statistical Analysis Plan.

- For categorical variables, the number and percentage of subjects/eyes within each category of interest will be presented.
- For continuous variables, the number of subjects/eyes with non-missing data, mean, standard deviation, range, median, minimum, and maximum. There will be no imputation for missing data.

All visual acuity results will be presented in logMAR scale after applying appropriate transformations/conversions.

Performance and safety outcome measures will be stratified by toric and non-toric models. Subjects who have been implanted with at least one toric IOL will be included in the toric group. Descriptive results from this long-term study should be sufficient to provide long-term data on these models, as well as safety and performance thresholds derived from the current State of the Art.

9 SAFETY AND ADVERSE EVENTS AND DEVICE DEFICIENCIES

9.1 General Information

An AE is any untoward medical occurrence, unintended disease or injury, or untoward clinical signs (including abnormal laboratory findings) in subjects, users, or other persons, whether or not related to the investigational medical device. Refer to the Glossary of Terms (Section 17.1) and figures below for categories of AEs and SAEs.

Figure 2. Categorization of All AEs

[figure not shown]
[figure not shown]

Figure 3. Categorization of All SAEs

Serious Adverse Events

Specific Events Relevant to this Protocol

In addition to reporting all AEs (serious and nonserious) meeting the definitions, the Investigator must report any occurrence of the following as an SAE:

- Cystoid macular edema
- Hypopyon
- Endophthalmitis
- Lens dislocation from posterior chamber
- Pupillary block
- Retinal detachment
- Secondary Surgical Interventions

Any other potentially sight-threatening event may also be considered serious based on the judgment of the Investigator and should be reported appropriately as delineated in Section 9.3.

Device Deficiencies

A device deficiency is an inadequacy of a medical device with respect to its identity, quality, durability, reliability, safety, or performance. A device deficiency may or may not be associated with subject harm (i.e., ADE or SADE); however, not all ADEs or SADEs are due to a device deficiency. The Investigator should determine the applicable category listed in the Device Deficiency eCRF for the identified or suspect device deficiency and report any subject harm separately. Examples of device deficiencies include the following:

- Failure to meet product specifications (e.g., incorrect IOL power)
- IOL defect
- Broken IOL optic
- Broken IOL haptic
- Scratched IOL optic
- Unsealed device packaging
- Suspected product contamination
- Lack of performance

9.2 Monitoring for Adverse Events

At Visit 1, after the subject has had the opportunity to spontaneously mention any problems, the Investigator should inquire about AEs by asking the standard questions shown below and report as applicable:

- “Have you had any health problems since your last study visit?”
- “Have there been any changes in the medicines you take because of a new health issue or worsening of an existing health issue since your last study visit?”

In addition, changes in any protocol-specific parameters and/or questionnaires evaluated during the study are to be reviewed by the Investigator. Any untoward (unfavorable and unintended) change in a protocol-specific parameter or questionnaire response that is clinically relevant, in the opinion of the Investigator, is to be reported as an AE. These clinically relevant changes will be reported regardless of causality.

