6.3 Evaluation Criteria / Effectiveness and Safety

The endpoints chosen align with those identified in the AcrySof IQ PanOptix Trifocal Intraocular Lenses State of the Art [REDACTED] Study assessments will be described in Section 7.3. Retrospective data will be collected from the pre-operative and surgical visits and any safety outcomes reported prior to enrollment. Prospective data will be collected at study enrollment 3 to 5 years (+/- 90 days) after IOL implantation.

6.3.1 *Primary Clinical Endpoint*

[figure not shown]

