9.3 Procedures for Recording and Reporting

AEs are collected from the time of initial exposure to the study model IOL(s) and throughout the course of the study. Any preexisting medical conditions or signs/symptoms present in a subject prior to exposure to the study model IOL(s) (i.e., before cataract surgery) are not considered AEs in the study and should be recorded in the Medical History section of the eCRF.

In addition, aqueous cells and flare, corneal edema, raised IOP and superficial punctate keratitis are examples of early post-operative findings that are typically observed following ocular surgery. These are not considered AEs if they can be reasonably expected to resolve within 2 weeks and not result in any untoward long term visual outcome impact.

For each recorded event, the ADEs and SAEs documentation must include: AE diagnosis of main symptom, date of occurrence, intensity (severity), treatment (if applicable), outcome, and assessments of the seriousness and causality. In addition, the Investigator must document all device deficiencies reported or observed with the medical devices on the Device Deficiency eCRF. The site must submit all available information on ADEs, SAEs, and device deficiencies to the study Sponsor immediately as follows:

- All SAEs must be reported immediately (within 24 hours) of the Investigator’s or site’s awareness.
- ADEs that do not meet seriousness criteria and device deficiencies must be reported within 10 calendar days of the Investigator’s or site’s awareness.
- A printed copy of the completed SAE and ADE and/or Device Deficiency eCRF must be included with product returns.

- Additional relevant information after initial reporting must be entered into the eCRF as soon as the data become available.
- Any changes to concomitant medications must be documented on the appropriate eCRFs.
- All relevant information from Discharge Summary, Autopsy Report, Certificate of Death etc., if applicable, must be documented in the narrative section of the SAE and ADE eCRF.

Study Sponsor representatives may be contacted for any protocol-related question and their contact information is provided in the Project Team Contact List included in the Investigator Site File.

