6.3 STATISTICAL METHODS FOR SAFETY ANALYSIS

The focus of the safety analysis will be to conduct a comprehensive descriptive assessment of AEs and other listed parameters in the safety analysis set and provide listings if necessary. Except otherwise stated, the analysis set for all safety analyses is the FAS as defined in Section 2.1. For this study, AEs from time of exposure to the study model IOL to the prospective study visit are considered.

All safety outcome measures will be stratified by the subgroups defined in section 10.4.

While imputation is not defined for this study, adverse events with partial AE dates will be considered for analysis if the AE occurs within the same month of implantation or if the AE can be determined as occurring after implantation using the partial date.

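### Both scripted adverse-event questions at Visit 1 are anchored to an earlier study visit that does not exist, so their recall period is empty or undefined and does not match the AE window that starts at lens implantation.

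*Protocol*

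**What the plan says.** Protocol Section 9.2 sets the time and order of the inquiry: "At Visit 1, after the subject has had the opportunity to spontaneously mention any problems", the investigator asks two standard questions. The first is "Have you had any health problems since your last study visit". The second asks about changes in medicines because of a new health issue or "worsening of an existing health issue since your last study visit".

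On the visit schedule, Section 7.7 defines compliance as "completing all the prospective assessments, which are anticipated to require a single study visit". In Table 3 (Section 7.6), consent, eligibility and every scheduled prospective assessment fall at Visit 1. The only other prospective column is the unscheduled visit, footnoted as "Prospective visit after Visit 1 to monitor subjects with ongoing AEs".

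On the AE window, Section 9.3 states "AEs are collected from the time of initial exposure to the study model IOL(s) and throughout the course of the study", and Section 7.3.18 says the same. SAP Section 6.3 analyses the matching period: "AEs from time of exposure to the study model IOL to the prospective study visit are considered". Section 6.3 of the protocol places Visit 1 in time: "Prospective data will be collected at study enrollment 3 to 5 years (+/- 90 days) after IOL implantation".

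Section 6.3.1.2 makes all AEs and device deficiencies the primary safety endpoints, drawn from Visit 1 and from retrospective data review.

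**The concern.** The script and the endpoint use different clocks. AEs count from implantation, but the subject is asked to recall from a study visit that never took place. Neither question in the available text mentions surgery or the lens.

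This matters because the direct question can reach events that the site's records may not hold. The documents allow for such events:

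- Recruitment extends to the surrounding metropolitan areas (Section 6.4.2).
- Investigators may be clinicians who provide only follow-up care (Section 13).
- Retrospective data are collected where available (Section 7.4).
- SAP Section 6.3.1.1 tabulates non-ocular AEs by subject, and an eye-clinic chart cannot be assumed to record several years of general illness or hospital admissions.

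An event that is never elicited leaves no gap in the data. The subject simply counts as event-free, and SAP Section 10.3 plans no imputation. Any error therefore lowers the reported AE percentages. Those percentages feed the benefit-risk objective (Protocol Section 5) and the comparison with state-of-the-art safety thresholds (Section 6.4.1). Remote monitoring is confined to the regulatory binder (Section 11.4), so it would not show that sites were asking about different periods.

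**Working it through.** The plan gives no figure for AE rates or for completeness of AE capture, so there is none to reproduce. Its one precision figure, the confidence-interval half-width for mean binocular BCDVA, is not affected. The check is a comparison of passages.

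**Step 1. Recall period in the script.** Both questions start at the last study visit (Section 9.2).

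**Step 2. Is there such a visit?** Scheduled visits before Visit 1: none (Table 3; Section 7.7). Unscheduled visits come after Visit 1 (Table 3, footnote a). Post-operative clinic visits appear in Table 3 under retrospective standard of care; they took place before consent and are not study visits. The anchor has no referent.

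**Step 3. Period the endpoint needs.** It runs from first lens exposure to Visit 1. With 90 days taken as about 3 months:

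- shortest: 3 years − 90 days ≈ 36 − 3 = 33 months
- longest: 5 years + 90 days ≈ 60 + 3 = 63 months

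**Step 4. Side by side.**

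| Source | Start | End |
|---|---|---|
| Script, read literally | none exists | Visit 1 |
| Script, read loosely | undefined, e.g. last clinic appointment | Visit 1 |
| Protocol 7.3.18 and 9.3 | first study-lens exposure | through the study |
| SAP 6.3 | lens exposure | Visit 1 |

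**Step 5. What still captures interval events.**

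- Chart review is a stated co-source (Sections 6.3 and 6.3.1.2; Table 3).
- Conditions starting at or after surgery must be recorded as AEs (Section 7.3.3).
- Spontaneous mention precedes the questions and has no recall limit (Section 9.2).
- Slit lamp, tonometry, dilated fundus examination, and capsulotomy history with date are done at Visit 1 (Sections 7.3.12 to 7.3.14).
- Concomitant medications are collected at Visit 1 (Table 3).

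What remains exposed is an event missing from the chart, not volunteered, and leaving no sign or medication.

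**Step 6. Illustration only.** Both the true event rate p and the share s of events captured by all routes together are assumptions. With 100 subjects in a group, the chance of recording at least one event is 1 − (1 − p × s)^100.

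| p | s = 100% | 80% | 50% | 20% |
|---|---|---|---|---|
| 1% | 63.4% | 55.2% | 39.4% | 18.1% |
| 3% | 95.2% | 91.2% | 77.9% | 45.2% |

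For example, p = 1% and s = 50% give 1 − 0.995^100 = 39.4%. The table shows how sensitive rare-event detection is to incomplete capture at this sample size. It does not say what s is, or how much of any shortfall would come from the question wording.

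**The case against.** The strongest reply is that the collection rule is stated correctly, twice, in Sections 7.3.18 and 9.3, and that site staff will follow it whatever the script says. Table 3, footnote c, also has AEs assessed at all post-operative visits through Visit 1 and entered in the database, and source documents are defined broadly enough to include hospital records (Section 10.2). On this view the questions are a slip of wording in a descriptive study with no safety hypothesis.

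Much of that stands, and it rules out three stronger readings that a reader might infer:

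- *That the interview is the only route to events treated elsewhere.* Step 5 lists other routes, and the documents do not say what outside correspondence the charts contain.
- *That subjects are never asked about the interval.* Staff or subjects may read the question broadly. Sections 7.3.16 and 7.3.17, the questionnaires, the AE form and the site worksheets are also not available, so the statement can be made only of the visible script.
- *That recall covers none of the 33 to 63 months.* This needs the literal reading, under which the question has no answer at all. Undefined is the accurate word for what happens in practice.

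The reply does not rescue the wording. A general instruction to staff does not tell the subject how far back to think, spontaneous mention is unprompted, and examinations can miss resolved or non-ocular events. If staff widen the question on their own initiative, the period asked about may differ between sites.

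**Conclusion.** The script is wrong as written. Both Visit 1 questions depend on a study visit that does not exist, and their recall period does not match the AE window of about 33 to 63 months. This conclusion rests only on the text of Protocol Sections 7.6, 7.7, 9.2 and 9.3 and SAP Section 6.3, and needs no assumption about rates.

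The consequence is narrower: possible under-elicitation, which may differ by site, of events that the other routes also miss. The direction is towards AE percentages that are too low. The size cannot be estimated, because the documents give neither an event rate nor a capture rate. They do not support saying that AEs from the 3 to 5 years go uncollected. Endpoints, sample size and analysis methods are unaffected.

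**What to change.** In both Visit 1 questions of Section 9.2, replace the last-study-visit anchor with: *since the surgery in which your first study lens was implanted (month/year)*, with the date filled in from the chart. This matches Sections 7.3.18 and 9.3 and SAP Section 6.3. Keep the present wording only for unscheduled visits after Visit 1, where there is an earlier study visit to refer to. Carry the change into any site worksheet that repeats the questions.

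Optional: a short prompt list, in lay terms, of the events named in Section 6.3.1.2. It may help recall but is not needed to remove the inconsistency.

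Cost: a wording amendment, which under Section 12 needs IRB/IEC approval before use, and about one more minute per visit.

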9.3 Procedures for Recording and Reporting

AEs are collected from the time of initial exposure to the study model IOL(s) and throughout the course of the study. Any preexisting medical conditions or signs/symptoms present in a subject prior to exposure to the study model IOL(s) (i.e., before cataract surgery) are not considered AEs in the study and should be recorded in the Medical History section of the eCRF.

In addition, aqueous cells and flare, corneal edema, raised IOP and superficial punctate keratitis are examples of early post-operative findings that are typically observed following ocular surgery. These are not considered AEs if they can be reasonably expected to resolve within 2 weeks and not result in any untoward long term visual outcome impact.

For each recorded event, the ADEs and SAEs documentation must include: AE diagnosis of main symptom, date of occurrence, intensity (severity), treatment (if applicable), outcome, and assessments of the seriousness and causality. In addition, the Investigator must document all device deficiencies reported or observed with the medical devices on the Device Deficiency eCRF. The site must submit all available information on ADEs, SAEs, and device deficiencies to the study Sponsor immediately as follows:

- All SAEs must be reported immediately (within 24 hours) of the Investigator’s or site’s awareness.
- ADEs that do not meet seriousness criteria and device deficiencies must be reported within 10 calendar days of the Investigator’s or site’s awareness.
- A printed copy of the completed SAE and ADE and/or Device Deficiency eCRF must be included with product returns.

- Additional relevant information after initial reporting must be entered into the eCRF as soon as the data become available.
- Any changes to concomitant medications must be documented on the appropriate eCRFs.
- All relevant information from Discharge Summary, Autopsy Report, Certificate of Death etc., if applicable, must be documented in the narrative section of the SAE and ADE eCRF.

Study Sponsor representatives may be contacted for any protocol-related question and their contact information is provided in the Project Team Contact List included in the Investigator Site File.

Further, depending upon the nature of the AE or device deficiency being reported, the study Sponsor (or designee) may request copies of applicable portions of the subject's medical records. The Investigator must also report all AEs and device deficiencies that could have led to a SADE according to the requirements of regulatory authorities or IRB/IEC.

Intensity and Causality Assessments

Where appropriate, the Investigator must assess the intensity (severity) of the AE based on medical judgment with consideration of any subjective symptom(s), as defined below:

Intensity (Severity)

- | | |
|-----------|--|
| Mild: | An AE is mild if the subject is aware of but can easily tolerate the sign or symptom. |
| Moderate: | An AE is moderate if the sign or symptom results in discomfort significant enough to cause interference with the subject's usual activities. |
| Severe: | An AE is severe if the sign or symptom is incapacitating and results in the subject's inability to work or engage in their usual activities. |

The Investigator must assess the causality for every AE in the study (Related or Not Related to the medical device or study procedure). An assessment of causality will also be performed by the study Sponsor utilizing the same definitions, as shown below:

Causality

- | | |
|---------|--|
| Related | An AE classified as related may be either definitely related or possibly related where a direct cause and effect relationship with the medical device or study procedure has not been demonstrated, but there is a reasonable possibility that the AE was caused by the medical device or study procedure. |
|---------|--|

Not Related An AE classified as not related may either be definitely unrelated or simply unlikely to be related (i.e., there are other more likely causes for the AE).

The study Sponsor will assess the AEs and may upgrade the Investigator's assessment of seriousness and/or causality. The study Sponsor will notify the Investigator of any AEs that is upgraded from nonserious to serious or from unrelated to related.

